# 485 STATISTICAL CONSIDERATIONS

# 486487 Sample Size Calculation and statistical analyses

The study will have an open label, randomised cross-over design. Randomisation will be for basal insulin alone. This is a pilot study as no previous studies have been performed

490 comparing basal insulins during long-haul travel. Given the novelty and practical

491 relevance of the study and our recent information about the challenges face by

492 individuals with T1D undertaking travel (see above) we believe that this project will have

- 493 a very high chance of publication in a high impact peer-reviewed journal.
- 494

495 The aim is to compare the impact of long-haul travel on glycemic control (CGM derived

data for time in range (**70-140 mg/dl**) as the primary end point with the assessment

497 during the **initial 24 hours** after arriving at EWR or JFK and HNL (starting within 2

hours after arrival) comparing Glargine U100 versus Degludec U100 as the basal
 insulin.

501	Primary Endpoint : time in 70 to 140 mg/dl after a long-haul flight from HNL to EWR
502	or JFK and from EWR or JFK to HNL during the initial 24 hours after arriving at EWR
503	or JFK and HNL (starting within 2 hours after arrival).
504	
505	Secondary CGM End-Points comparing Glargine and Degludec as the basal insulin):
506	• Time in range (70-180 mg/dl) within the first 24 hours after arriving in HNL and
507	EWR or JFK (starting within 2 hours after arrival).
508	• Mean + SD CGM glucose (mg/dl)
509	• % CGM time <50 mg/dl
510	• % CGM time <60 mg/dl
511	• % CGM time $<70$ mg/dl
512	• % CGM time 70–180 mg/dl
513	• % CGM time >180 mg/dl
514	• % CGM time >250 mg/dl
515	• % CGM time >300 mg/dl
516	• SD and coefficient of variation of CGM values
517	• Fasting BG at 0600 local time, using CGM
518	• Additionally, new CGM BG ranges will be included as consensus guidelines
519	emerge, including but not limited to those from the 2019 Advanced Technologies
520	and Treatments for Diabetes International Consensus on Time in Range (29):
521	• % CGM time 54–69 mg/dl
522	
 
% CGM time <54 mg/dl
 

523	
524	Comparisons will be made for
525	• Total travel
526	
 
Total East to West travel and West to East travel
 

527	• 24 hours prior to each flight
528	• During each flight (total time, from take-off to meal and from meal to landing)
529	• 24, 48 and 72 hours at the destination
530	
531	In addition the secondary end-points will be compared for Glargine and Degludec for
532	specific time blocks to assess the contribution from each basal insulin:
533	A. Between 2200 and 0700 hours the night before each flight
534	B. Between 2200 and 0700 hours for Days 2 and 3 at each destination
535	For the purpose of our primary outcome data CGM data will primarily be obtained from
536	the Abbott FreeStyle Libre Pro system, but in the case of missing data, we will also
537	evaluate any secondary personal CGM data.
538	
539	Sample size for this pilot study is based on recent data indicating that individuals with
540	type I diabetes spend approximately $669\pm208$ minutes between /0-180 mg/dl (26). With
541 542	the criterion for significance set at 0.05, and using a paired t-test analysis, a sample size of 22 subjects will achieve a power of at least $800/$ to detect a difference of $100/$ between
342 542	basel insuling assuming the standard deviation of the difference is <106 minutes (Table
545 511	1 Although Battelino et al (26) reported the standard deviation of the target
544 575	neasurement it did not report the standard deviation of the difference in the
545	measurement, it did not report the standard deviation of the difference in the

- 546 measurements. Since this is unknown, yet needed for the power calculation, an estimate
- 547 was derived using the two treatment groups reported by the Battelino et al (26) using
- 548 Altman (27). This derivation yielded a value of 25.7. It is acknowledged that the two
- 549 treatment groups reported by Battelino et al (26) are different than those investigated in 550 this protocol (and the groups were independent rather than paired), but since similarities
- exist the derived estimate is sufficient for preliminary power calculations. Table 1
- reports that when the standard deviation of the difference is 25, this investigation will
- have over 99% power to detect a difference between the two insulin groups. Since 25 is a
- by low estimate, Table 1 also reports standard deviation estimates up to 110, and reports that
- 555 >80% power is achieved up to 106 but <80% when the standard deviation of the
- 556 difference is >106. Assuming that the standard deviation of the difference in this
- 557 investigation will be  $\leq 106$  minutes is justified given that the value of this standard
- deviation in a previous study (26) is 25.7 which is well below the 106 threshold. In
- anticipation of potential drop-outs 25 subjects will be recruited.
- 560

561 **Table 1:** Power obtained under a range of various assumptions for the Standard

- 562 Deviation of the Difference
- 563

Alpha	0.05	0.05	0.05	0.05	0.05	0.05	0.05
Sample Size	22	22	22	22	22	22	22
-							
Effect Size	2.680	0.893	0.670	0.638	0.632	0.626	0.609
Mean Difference	67	67	67	67	67	67	67
SD of Difference	25	75	100	105	106	107	110
Power	>99%	97.89	84.99	81.42	80.69	79.96	77.76

564

565 Comparisons will be made using Student's paired *t*-tests (two-sided) for normative and log-transformed data, Wilcoxon signed rank testing for non-parametric data, and N1 chi-566 567 square tests for proportions (30). Data will be expressed wherever possible as mean 568 difference with 95% confidence limits for the difference or as mean + standard error or 569 deviation for the difference. For non-parametric data, these will be presented as median 570 differences with inter-quartile ranges. All data will be analysed on an intention to treat 571 basis. No interim analysis is anticipated. Furthermore, to gain as much information as 572 possible from this pilot study, all hypotheses will be tested at 0.05 and no adjustments for 573 multiplicity will be made.

574

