#### 127 **Endpoints**:

128 The **Primary endpoint** will be, using continuous interstitial glucose monitoring (CGM),

129 achieved glycemic control defined as time in range (70-140 mg/dl) during the initial 24 130 hours local time (starting within 2 hours after arriving) in Newark, NJ or JFK, NY after

131 flying 9-10 hours West to East (from Honolulu, HI) and after the return journey from

132 Newark to Honolulu (flying East to West) comparing Glargine U100 versus

- 133 DegludecU100 as the basal insulin.
- 134

135 Participants will begin in Honolulu, HI (HNL), fly to Newark (EWR) or New York (JFK)

- 136 where they will stay for up to 72 hours followed by a return long-haul flight back to
- 137 Honolulu with up to 72 hours at this destination. This journey will be repeated after a 2
- 138 week period when subjects return to their original insulin treatment regimen and then
- 139 switch to the alternative basal insulin. When traveling east, the day gets shorter, so the

140 basal insulin dose given during travel needs to be adjusted (see below).

141

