#### 142 Figure 1. Overview of protocol with Primary and Secondary endpoint timelines for

#### 143 assessment. This journey will be undertaken twice - once using Glargine U100 and

- 144 once using Degludec as the basal insulin.
- 145

P = Primary End Point : Time in range (70-140 mg/dl) during the initial 24 hours local time (starting within 2 hours after arriving in Newark (EWR)/ New York (JFK) from Honolulu (HNL) and after the return journey from EWR/JFK to HNL).

146 147

154

148 Secondary CGM End-Points comparing Glargine U100 and Degludec as the basal 149 insulin are based on recent consensus related to reporting of trials for artificial pancreas 150 development (17):

- 151 Time in range (70-180 mg/dl) within the first 24 hours after arriving in HNL and • 152 EWR or JFK (starting within 2 hours after arrival). 153
  - For the inflight period of time and for the 72 hours in each destination:
    - $\circ$  Mean +SD CGM glucose (mg/dl)

155	○ % CGM time <50 mg/dl
156	$\circ$ % CGM time <60 mg/dl
157	○ % CGM time <70 mg/dl
158	$\circ$ % CGM time 70–180 mg/dl
159	$\circ$ % CGM time >180 mg/dl
160	$\circ$ % CGM time >250 mg/dl
161	$\circ$ % CGM time >300 mg/dl
162	• SD and coefficient of variation of CGM values
163	• Fasting BG at 0600 local time, using CGM
164	• Additionally, new CGM BG ranges will be included as consensus guidelines
165	emerge, including but not limited to those from the 2019 Advanced Technologies
166	and Treatments for Diabetes International Consensus on Time in Range (29):
167	• % CGM time 54–69 mg/dl
168	$\circ$ % CGM time <54 mg/dl
169	
170	Secondary non-CGM derived endpoints will be (a) Fear of hypoglycemia (HFS II) (18)
171	and Hypoglycemic Confidence Scale (28), (b) Liverpool Jet-Lag Questionnaire (19), (c)
172	Salivary cortisol and melatonin and (d) Sleep duration and quality and (e) Activity
173	(ActiGraph, LLC, Florida) (20).
174	
175	
176	STUDY DESIGN
177	
177 178	This study will be an open-label, single center, pilot study randomized to either Glargine
177 178 179	This study will be an open-label, single center, pilot study randomized to either Glargine or Degludec as the basal insulin, and then a 2 week break, followed by a cross-over to the

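### The stated 80% power for a 10% difference is derived from time in 70-180 mg/dl, a secondary endpoint, and is not established for the primary endpoint, time in 70-140 mg/dl

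*Combined protocol and SAP*

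**What the plan says.** **Primary endpoint.** The Endpoints section defines "achieved glycemic control defined as time in range (70-140 mg/dl) during the initial 24" hours after arrival. It covers the outbound flight "West to East (from Honolulu, HI) and after the return journey from" the New York area, so there are two arrival windows. The legend to Figure 1 repeats the definition: "P = Primary End Point : Time in range (70-140 mg/dl) during the initial 24 hours local time". Under Sample Size Calculation and statistical analyses, the 70-140 range is again named "as the primary end point with the assessment" in the initial 24 hours.

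**Secondary endpoint.** The list of Secondary CGM End-Points opens with "Time in range (70-180 mg/dl) within the first 24 hours after arriving in HNL and" the New York area.

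**Basis for n.** The same statistical section rests the sample size on 669±208 "minutes between /0-180 mg/dl (26). With". It then claims at least 80% power with 22 subjects to detect a 10% difference by a paired t-test at 0.05, provided the SD of the difference does not exceed 106 minutes. Table 1 uses a mean difference of 67 minutes in every column. The text reads the table as showing that "80% power is achieved up to 106 but <80% when the standard" deviation of the difference is larger.

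**Caveats given.** The plan calls the study a pilot and its power calculation preliminary. It says that the groups in the cited study "are different than those investigated in" this protocol, and that they were independent rather than paired. It does not mention that the glucose range differs from that of the primary endpoint.

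**The concern.** A reader will take the power claim as describing the primary comparison. Its inputs describe a different endpoint. Time in 70-140 is nested inside time in 70-180, so its mean and its variability may both differ, and the plan supplies neither.

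The practical stake is how a null primary result would be read. With a stated 80% power for a 10% difference, such a result could be taken as coming from a test sized for that difference, when no figure in the plan supports this for 70-140. The planned analysis and data collection are not affected.

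**Working it through.** **Inputs** (Sample Size Calculation and statistical analyses, and Table 1): mean 669 minutes and SD 208 for time in 70-180; difference 67 minutes; two-sided alpha 0.05; paired t-test; n = 22, with 25 recruited; assumed ceiling of 106 for the SD of the difference; 25.7 derived from the cited study. For 70-140 there are no inputs.

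**1. Where the 67 minutes comes from.** 0.10 × 669 = 66.9, rounded to 67; 67/669 = 10.0%. The target is 10% of the 70-180 mean.

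**2. Reproducing Table 1.** Power = P(|T| > t(0.975, n−1)), where T is noncentral t with n−1 degrees of freedom and noncentrality (difference/SD) × √n.

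| SD of difference | 75 | 100 | 105 | 106 | 107 | 110 |
|---|---|---|---|---|---|---|
| Table 1, % | 97.89 | 84.99 | 81.42 | 80.69 | 79.96 | 77.76 |
| Recomputed, % | 97.89 | 84.99 | 81.43 | 80.70 | 79.97 | 77.76 |

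The table is right to within 0.01 point. It contains only minutes, so it holds for any endpoint with these values.

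**3. A condition that needs no assumed mean.** The standardised effect giving 80% power is 0.6264 at n=22 and 0.5840 at n=25. For a 10% difference, the largest SD of the difference as a share of the endpoint's mean is:

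- n=22: 10/0.6264 = 16.0%
- n=25: 10/0.5840 = 17.1%

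On 70-180, 106/669 = 15.8%, so the condition is met only if the assumed ceiling of 106 holds. If both periods have SD 208, an SD of the difference of 106 implies a within-person correlation of 1 − 106²/(2 × 208²) = 0.87. At an assumed correlation of 0.5 the SD of the difference is 208, and power for 67 minutes at n=22 is 30%. The 80% is thus conditional for 70-180 too. For 70-140 the ratio cannot be formed.

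**4. What the ceiling of 106 would require of the primary.** Mean needed = 106 × 0.6264/0.10 = 664 minutes at n=22, and 106 × 0.5840/0.10 = 619 minutes at n=25. The plan states no such mean. At 25.7 the mean needed at n=22 is only 25.7 × 0.6264/0.10 = 161 minutes.

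**5. Illustration only.** Assume a 70-140 mean of 50-90% of 669 in one 24-hour window (not from the documents). The last column averages two windows, each with SD 106 and with uncorrelated differences, so that the SD is 106/√2 = 75.0.

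| Mean, % of 669 | 10% target, min | 67 min as % of mean | Largest SD for 80%, n=22 / n=25 | Power at SD 106, one window, n=22 / n=25 | Power, two windows averaged, n=22 |
|---|---|---|---|---|---|
| 50 | 33.5 | 20.0 | 53.4 / 57.3 | 29.2% / 32.8% | 51.5% |
| 60 | 40.1 | 16.7 | 64.1 / 68.7 | 39.6% / 44.3% | 66.9% |
| 70 | 46.8 | 14.3 | 74.8 / 80.2 | 50.7% / 56.4% | 79.8% |
| 80 | 53.5 | 12.5 | 85.4 / 91.6 | 61.8% / 67.8% | 89.1% |
| 90 | 60.2 | 11.1 | 96.1 / 103.1 | 71.9% / 77.8% | 94.9% |

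If instead the SD falls in proportion to the mean, power is 80.6% at n=22 (85.7% at n=25) in every row. At an SD of 25.7 it exceeds 99% in every row. The documents do not say which case applies.

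**The case against.** The strongest defence is that Table 1 is an absolute statement: 67 minutes, with an SD of the difference up to 106, gives 80% power whatever the glucose range. That stands. What does not transfer is the 10% label, because 67 minutes is 10% only of the 70-180 mean.

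Second, the plan's derived SD of 25.7 would leave ample room on almost any mean. That also stands as arithmetic, but the plan itself treats the value as low, obtained it from independent groups, and sets its claim at 106.

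Third, this is a self-described pilot that prints both ranges openly. That lowers the consequence. It does not close the gap, since the plan still states a directional hypothesis, tests at 0.05 and claims 80% power, and its caveats do not mention the range.

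A reader might go further and infer that the primary comparison is underpowered. The documents do not support this. The low powers in the illustration come from lowering the mean while holding the SD at a break-even value, in a single window. Nor does the nesting settle the matter. In the cited study's population, over the same period, time in 70-140 cannot exceed 669 minutes. That bound does not carry over: the cited study was in pump therapy (References, item 26), and current pump users are excluded here (Exclusion Criteria, item 1).

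**Conclusion.** The concern holds as a gap in the stated basis for n. Both endpoint definitions, the planning mean and the origin of the 67 minutes are on the page, and no planning value for 70-140 is.

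Its size is best expressed by the ratio condition of 16.0% of the mean at n=22 and 17.1% at n=25. This rests only on a two-sided paired t-test at 0.05 with normally distributed differences. As a ratio it applies whether the two arrival windows are summed, averaged or tested separately; in the last case it gives power per test. It would also be wrong to infer that the plan has secured 80% power on 70-180, since 106 is an assumed ceiling and not an estimate. The point should be fixed, but it calls for a correction to the justification, not to the design.

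**What to change.** Preferably, restate the power paragraph and Table 1 under Sample Size Calculation and statistical analyses for time in 70-140 mg/dl. Give an explicitly assumed mean, labelled as assumed; the target in minutes with its relative size; a range of SDs of the difference; and whether the figures cover one 24-hour window or both arrivals combined.

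Alternatively, keep Table 1 and replace the claim with:

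> With 22 subjects there is at least 80% power to detect a 67-minute difference if the SD of the difference is at most 106 minutes; 67 minutes is 10% of the mean reported for 70-180 mg/dl, a secondary endpoint, and no power for a 10% difference is claimed for the primary endpoint, time in 70-140 mg/dl.

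The cost is one table on labelled assumptions, or one sentence. The stated power for the primary may become less favourable. No extra patients or data are needed.

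### Signed-rank comparisons are to be shown as median difference with inter-quartile range, so they have no planned confidence interval for the treatment effect

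*Combined protocol and SAP*

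**What the plan says.** The relevant text is the closing paragraph of Statistical Considerations, under Sample Size Calculation and statistical analyses. It assigns paired t-tests (two-sided) to normal and log-transformed data and "Wilcoxon signed rank testing for non-parametric data".

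Results are then to be expressed, where possible, as the mean "difference with 95% confidence limits for the difference or as mean + standard error or" deviation of the difference. The other branch reads "For non-parametric data, these will be presented as median" "differences with inter-quartile ranges".

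No other section plans a confidence interval for a signed-rank comparison. The plan also gives no rule for deciding which endpoints count as non-parametric. It adds that "all hypotheses will be tested at 0.05 and no adjustments for" multiplicity will be made.

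**The concern.** The plan offers an interval estimate in one branch and only a measure of spread in the other. In a pilot, a later trial will mainly need the estimated effect and its precision. The plan lists many CGM endpoints over many time windows, all tested at 0.05 without adjustment. Where the only interval shown is an IQR, readers cannot tell which treatment effects the data exclude, and they are left with unadjusted p-values.

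The endpoints most likely to be affected are the percentages of time at very low or very high glucose (below 50, 54, 60 or 70 mg/dl, above 250 or 300 mg/dl). Over a single flight or 24 hours these could well be skewed with many zeros. That is an expectation and not a figure in the documents. With no rule for choosing the test, the primary endpoint could also end up in this branch.

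A second mismatch is that the sample median of the paired differences is not the quantity the signed-rank test addresses. That quantity is the pseudo-median, estimated by the median of all pairwise (Walsh) averages.

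**Working it through.** **Inputs** (sample-size text and Table 1): 22 pairs; mean difference 67 min; SD of the difference 25 to 110 min, with 106 as the limit for 80% power and 25.7 as the plan's derived value; alpha 0.05 two-sided.

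**1. The plan's own figure.** Power of the paired t-test uses the noncentral t with 21 df and noncentrality (67/106) × √22 = 2.965, critical value 2.080. This gives 80.70%, against 80.69% in Table 1. SDs of 75, 100, 105, 107 and 110 also reproduce to within 0.01 percentage points, so the inputs are read correctly.

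**2. What each interval measures** (normal differences, SD 106, n = 22).
- Population IQR width: 2 × 0.6745 × 106 = 143 min. No n appears in the formula. The mean sample IQR in simulation is about 134 min.
- t-based 95% CI width: 2 × 2.080 × 106/√22 = 94 min. This narrows with √n.
- Hodges-Lehmann 95% CI: there are 22 × 23/2 = 253 Walsh averages. The exact test rejects when the smaller rank sum is 65 or less (two-sided level 0.046), so the limits are the 66th smallest and 66th largest averages. Mean simulated width is about 96 min.

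**3. The two displays on one constructed sample** (22 normal quantiles scaled to mean 67, SD 106).
- Planned display: median 67, IQR −2.4 to 136.4, signed-rank p = 0.009.
- Matched display: Hodges-Lehmann estimate 67, 95% CI 16.4 to 117.6.

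**4. How often the IQR spans zero among significant signed-rank results.** This is simulated with normal differences, mean 67 min, n = 22.

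| SD of difference (min) | Share with IQR spanning zero |
|---|---|
| 25.7 | about 0% |
| 50 | under 1% |
| 75 | 15% |
| 100 | 32% |
| 106 | 36% |

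In normal samples the Hodges-Lehmann interval agreed with the test every time. This table is illustration only: the plan sends normal data to the t-test, and the inputs are minutes in range rather than the skewed percentages.

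**5. A zero-heavy sample** (assumed, 22 pairs: 14 differences of 0 and 8 negative, from −0.5 to −5 percentage points).
- Planned display: median 0, IQR −1.4 to 0.
- Signed-rank p with zeros dropped: 2 × (1/2)^8 = 0.008.
- Of the 253 Walsh averages, 14 × 15/2 = 105 are zero and 148 are negative. The 127th, the Hodges-Lehmann estimate, is −0.5. The 66th largest is 0, so the standard interval is −1.5 to 0 and touches zero beside p = 0.008.
- With 16 zeros and 6 negatives (−0.5 to −3), the median is 0, the IQR is −0.375 to 0 and p = 2 × (1/2)^6 = 0.031. The standard interval again ends at 0.

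**6. Why zeros need a rule.** In the 14-zero sample, test a shift just below zero. The 14 zeros become small positive values holding ranks 1 to 14, with sum 14 × 15/2 = 105. That exceeds 65, so the shift is not rejected. Zero itself is rejected (p = 0.008). If the same zero rule is used in the test and in its inversion, the interval therefore runs up to zero but excludes it, and the two agree. If zeros are dropped for the test and kept in the Walsh averages, they appear to disagree.

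**The case against.** Several counter-arguments are sound, and they limit the point.

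- **Contradiction.** A reader might infer that the planned display can contradict its own test. It cannot. An IQR makes no claim about a zero effect, so a small p-value beside an IQR spanning zero is no more contradictory than a mean ± SD spanning zero.
- **The 36% figure.** A reader might take this as the expected rate of confusing displays. It comes from normal data, which the plan sends to the t-test, and from the least favourable SD at which 80% power still holds. At the plan's derived SD of 25.7 the share is about zero.
- **Hypoglycemia.** A reader might infer that the hypoglycemia comparison will certainly lack a measure of precision. The documents do not say so. Skewed endpoints may be log-transformed and then receive a confidence interval, although exact zeros would complicate that route.
- **SE or SD in the parametric branch.** The SE is itself a measure of precision, and either the SE or the SD of the difference converts to a paired-t interval once n is known. That wording is untidy rather than a loss of information.
- **The remedy.** The usual Hodges-Lehmann interval can itself end at zero beside a significant test when zeros are common, as step 5 shows. This objection stands and shapes the fix.

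The gap remains after all of this: the signed-rank branch has a stated display, and that display contains no measure of precision for the treatment effect.

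**Conclusion.** The point holds as a reporting weakness. Every comparison analysed by the signed-rank test lacks a planned confidence interval, and its displayed median is not the quantity tested. It does not affect sample size, power or type I error.

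The number of endpoints affected is unknown, because the plan neither lists the non-parametric endpoints nor says how they will be identified. The low- and very-high-glucose percentages are plausible candidates if not log-transformed. At SD 106 and n = 22, the population IQR is about one and a half times as wide as the matched interval (143/96 = 1.49), and it would stay 143 min wide in a larger trial.

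These figures assume normal differences, and the zero-heavy samples are assumed. I read the IQR as that of the individual paired differences, which is the natural reading of the sentence.

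**What to change.** In the closing paragraph of the statistical section:

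1. For each signed-rank comparison, report the Hodges-Lehmann estimate (median of the Walsh averages) with a 95% CI from inverting the same signed-rank test.
2. State one rule for zeros and ties, for example Pratt ranking or an exact permutation version, and use it in both the test and the interval. Say whether a limit equal to zero belongs to the interval.
3. Keep the median and IQR of the differences as description only.
4. For mean differences, always give the 95% CI, with SE or SD as an addition and not an alternative.

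The cost is revised wording, slightly more programming for zeros and ties, and somewhat fuller tables. No change to design, recruitment or data collection is needed.
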